3.3.2 Exclusion Criteria

To be eligible for entry into the study, the subject must not meet any of the exclusion criteria listed below:

- 1. Clinically significant acute or chronic liver disease unrelated to NASH, including but not limited to primary sclerosing cholangitis (PSC), Wilson's disease, alpha-1 antitrypsin (AAT) deficiency (MZ or ZZ phenotype), hepatitis B or C, hereditary hemochromatosis, alcoholic liver disease, and drug induced liver disease.
- 2. Clinically or histologically documented cirrhosis.
- 3. Poorly controlled T2DM (HbA1c ≥9.5%) or Type 1 Diabetes Mellitus.
- 4. Hepatitis B surface antigen positive.
- 5. Hepatitis C antibody positive with active infection.
- 6. Human immunodeficiency virus (HIV)-1 or HIV-2 infection.
- 7. Glucose-6-phosphate dehydrogenase (G6PD) deficiency.
- 8. Any prior history of hepatic decompensation (encephalopathy, ascites, gastroesophageal varices, hepatorenal syndrome), platelet count <150,000/mm³, international normalized ratio (INR) ≥1.3 despite vitamin K supplementation, serum albumin <3.2 g/dL, or a prior or planned liver transplantation.
- 9. History of alcohol or substance abuse or dependence.
- 10. Hepatic steatosis that, in the opinion of the Investigator, is primarily related to alcohol consumption.
- 11. Inability to undergo MRI for any reason.

Note: Mild sedative use (if not prohibited as described in Section 4.6 of the protocol) for MRI procedures is permitted.

- 12. Laboratory parameters within any of the following ranges:
 - AST >5 × ULN.
 - ALT ≥5 × ULN.
 - Estimated glomerular filtration rate (eGFR) <60 mL/min/1.73 m².
 - Hemoglobin <11 g/dL for males or females.
 - Direct bilirubin <LLN or >ULN.
 - Total bilirubin <LLN or >ULN.

Note: Total bilirubin >ULN due to Gilbert's syndrome is acceptable provided that direct bilirubin, reticulocyte count, and hemoglobin are within the laboratory defined normal ranges.

• Thyroid-stimulating hormone (TSH) <LLN or >1.5 \times ULN.

Note: Subjects on a medication for a thyroid abnormality may enroll provided that they have been maintained on a stable dose for ≥ 90 days prior to randomization.

- 13. Current use of oral prednisone/prednisolone (or prednisone/prednisolone equivalent) >10 mg/day.
- 14. History of myocardial infarction, congestive heart failure, uncontrolled cardiac arrhythmia, unstable angina, coronary bypass surgery, or percutaneous coronary intervention ≤12 months prior to Screening.
- 15. History of malignancy ≤2 years prior to Screening or ongoing malignancy other than basal cell carcinoma, or resected noninvasive cutaneous squamous cell carcinoma.
- 16. Active, serious infections that require parenteral antibiotic or antifungal therapy ≤30 days prior to Screening.

- 17. Major surgical procedure ≤30 days prior to Screening or prior organ transplantation.
- 18. Current or anticipated treatment with radiation therapy, cytotoxic chemotherapeutic agents, and immune-modulating agents.
- 19. Current use of prohibited medications as described in Section 4.6 of the protocol.
- 20. Females who are pregnant or breastfeeding.
- 21. Allergy to the study drug or its components.
- 22. Use of any unapproved treatment for NASH, including but not limited to UDCA and berberine containing agents, ≤30 days prior to Screening.
- 23. Participation in other clinical trials of investigational drugs for NASH ≤6 months prior to Screening.
- 24. Received any investigational drugs for any other condition ≤30 days or 5 half-lives (whichever is longer) prior to Screening.
- 25. Any other clinically significant laboratory parameters, disorders, or prior or current therapy that, in the opinion of the Investigator, would make the subject unsuitable for the study, unable to comply with the dosing and protocol requirements, or could confound the study outcomes.

3.4 ENDPOINTS

3.4.1 Efficacy

3.4.1.1 Primary Endpoint

The primary endpoint for this study is the absolute change in LFC as measured by MRI-PDFF from Baseline to Week 18. Analysis of the primary endpoint is described in Section 9.2.3.1.

3.4.1.2 Secondary Endpoints

The secondary endpoints of this study include the following:

- 1. Changes in fasting glucose and HbA1c from Baseline to Week 18.
- 2. Proportion of subjects who achieve ≥30% relative reduction in LFC as measured by MRI-PDFF from Baseline to Week 18.
- 3. Relative change in LFC as measured by MRI-PDFF from Baseline to Week 18.
- 4. Proportion of subjects who normalize LFC to <5% as measured by MRI-PDFF at Week 18.
- Proportion of subjects who achieve ≥5% absolute reduction in LFC as measured by MRI-PDFF from Baseline to Week 18.
- 6. Change in homeostasis model assessment-estimated insulin resistance (HOMA-IR) from Baseline to Week 18.
- 7. Change in LDL-c from Baseline to Week 18.
- 8. Change in serum triglycerides from Baseline to Week 18.
- 9. Change in HDL-c from Baseline to Week 18.
- 10. Changes in AST and ALT from Baseline to Week 18.
- 11. Proportion of subjects with elevated ALT at Baseline who normalize ALT at Week 18.
- 12. Change in Pro-C3 from Baseline to Week 18 for subjects with elevated Pro-C3 at Baseline.
- 13. Change in the enhanced liver fibrosis (ELF) score and each component of ELF (tissue inhibitor of metalloproteinases 1 [TIMP-1], N-terminal pro-peptide of type III collagen [PIIINP], and hyaluronic acid [HA]) from Baseline to Week 18.
- 14. Changes in total bile acids, 7α -hydroxy-4-cholesten-3-one (C4), and fibroblast growth factor 19 (FGF19) from Baseline to Week 18.

Analysis of the secondary endpoints is described in Section 9.2.3.2.

3.4.2 Safety

Adverse events and changes in physical examination, vital signs, electrocardiogram (ECG), and clinical laboratory values will be used to evaluate safety and tolerability. Adverse event incidence will be determined during the Double-Blind Treatment Period. Adverse event type, relationship, severity, onset, and duration will be presented by treatment group within the Double-Blind Treatment Period.

3.5 SUBJECT NUMBERING, RANDOMIZATION, AND BLINDING

After signing the ICF, subjects will be assigned a unique subject ID number, which is a combination of the investigational site ID number and a sequential subject number. The subject ID number will be maintained throughout the course of the study and will be the primary number used to manage subject-related operations and documentation. The process for subjects who fail Screening but then repeat the Screening process due to a change in their eligibility status (see Section 5.1.1) will be described in the Study Procedures Manual (SPM) or other applicable instructions.

Upon confirmation of subject eligibility at the Baseline visit (see Section 5.1.2), investigational site staff will login to the designated automated system to randomize the subject. Subjects will be randomized in equal numbers to 1 of 3 treatment groups: HTD1801 500 mg BID, 1,000 mg BID, or placebo BID. In addition to the subject ID number, subjects will be assigned a randomization number, as well as a kit ID number corresponding to a pre-packaged and numbered study drug kit (see Section 4.1.2).

All subjects and study personnel will remain blinded to the treatment administered throughout the study. All study drugs will be provided in matching white tablets, 4 tablets to a pouch, 2 pouches to be administered each day, 1 pouch in the morning and 1 pouch in the evening. An adequate supply of study drug will be provided to each subject at each clinic visit to cover the next 2- or 4-week period with additional days of coverage, as applicable (e.g., to provide for possible scheduling conflicts).

In this double-blind study, if a medical emergency occurs and a decision about a subject's condition requires knowledge of the study drug assignment in order to properly treat the subject, the study blind may be broken for that specific subject only. The decision to break the blind for a subject should only be made after consultation with the Medical Monitor or Sponsor representative.

Any broken blind must be clearly justified and explained by a note in the subject's source documents.

3.6 REPLACEMENT OF DROPOUTS

Subjects who do not complete the Double-Blind Treatment Period may be replaced at the Sponsor's discretion.

4.0 STUDY DRUGS AND DOSAGES

4.1 IDENTIFICATION AND DESCRIPTION OF INVESTIGATIONAL PRODUCT

4.1.1 Investigational Product

The HTD1801 drug substance, berberine ursodeoxycholate, is the salt formed between BBR and UDCA with a stoichiometry of 1:1. The HTD1801 drug product is a film-coated tablet containing 250 mg of berberine ursodeoxycholate. HTD1801 is expected to dissociate into BBR salt and UDCA after oral administration.

4.1.2 Labeling

The study drugs (HTD1801 500 mg, HTD1801 1,000 mg, and placebo) will be supplied by HighTide and packaged into polyethylene terephthalate/aluminum foil/polyethylene (PET/AL/PE) pouches. Each pouch will contain 4 HTD1801 250 mg and/or HTD1801-matching placebo tablets and be affixed with a single-panel label that will describe the following information at a minimum: study drug, dose, kit number, Sponsor name, instructions for storage between 36°F and 46°F (2°C and 8°C), and includes the statements "Caution: New Drug - Limited by United States law to investigational use" and "Keep out of reach of children."

An adequate supply of pouches will be placed into kits packaged for weekly use, and each subject will receive the appropriate number of kits to provide enough supplies until their next scheduled visit to the investigational site. Each kit will bear a label describing the following information at a minimum: kit number, Sponsor name, instructions for storage between 36°F and 46°F (2°C and 8°C), and includes the statements "Caution: New Drug - Limited by United States law to investigational use" and "Keep out of reach of children."

4.2 DOSING INSTRUCTIONS AND SCHEDULE

Subjects are instructed to take the entire contents of 1 pouch of study drug each morning and each evening with water and food (e.g., meal or snack) during the Double-Blind Treatment Period. Each pouch will contain 4 identical white tablets. Subjects should retain the empty pouches and return them to the investigational site on their next visit

along with any unused study drug. Returned unused study drug must not be re-dispensed to subjects.

4.3 HANDLING OF INVESTIGATIONAL PRODUCT

The Investigator will be fully responsible for the security, accessibility, and storage of the study drugs while they are at the investigational site. The Investigator is also responsible for the education of site staff in the correct administration of the study drugs and must ensure that appropriate study drug accountability records are maintained.

4.4 COMPLIANCE WITH INVESTIGATIONAL PRODUCT

At applicable clinic visits during the Double-Blind Treatment Period (see Section 5.1.3), subjects will be queried about their compliance with taking their assigned study drug as instructed. The number of full and empty study drug pouches will be captured on the electronic case report form (eCRF).

4.5 CONCOMITANT MEDICATIONS

The use of permitted concomitant medications may continue during the study at the same dosage strength and frequency. If subjects are receiving permitted medications, doses and regimens should be stable as described in Section 3.3.1:

- Thiazolidinediones, GLP-1 agonists, DPP-4 inhibitors, or SGLT-2 inhibitors must be stable for ≥90 days prior to randomization;
- Vitamin E dose of ≤400 IU must be stable for ≥90 days prior to randomization with no anticipated dose increases during the study;
- Regimens for other concomitant medications must be stable for ≥28 days prior to randomization.

Changes to permitted concomitant medications are not to be made unless medically necessary. The Medical Monitor may be consulted, as needed, on such changes. The need for medication or dose changes must be documented in the subject's source documents (e.g., in response to an AE).

During the Double-Blind Treatment Period, concomitant medications should not be taken within 1 hour prior to dosing of study drug or up to 6 hours following dosing of study drug.

Note the following for specific concomitant medications:

- Dose adjustments for T2DM medication regimens, including those for metformin and insulin, will primarily be made in consultation with the subject's primary care physician.
- Short courses of oral prednisone/prednisolone (or prednisone/prednisolone equivalent) ≤10 mg/day for conditions unrelated to NASH (e.g., allergic reaction) are permitted.
- The study drug should be taken >1 hour before or 4-6 hours after taking any of the following: bile acid sequestering agents (e.g., cholestyramine and colestipol), aluminum-based antacids (e.g., aluminum hydroxide), or traditional Chinese medicines.
- Based on HTD1801 human PK data and *in vitro* inhibition of cytochrome P450 (CYP450) and uridine diphosphate glucuronosyltransferase (UGT) enzymes, a meaningful inhibition of CYP2D6, CYP3A4, and UGT enzymes at the doses used in this study is not expected. Other than those listed in Section 4.6, Table 4, the concomitant use of statins, selective serotonin reuptake inhibitors, serotonin and norepinephrine reuptake inhibitors, and other antidepressants (i.e., agomelatine, mirtazapine, reboxetine, vilazodone, and vortioxetine) is permitted.

4.6 PROHIBITED CONCOMITANT MEDICATIONS

Certain concomitant medications have been identified for **exclusion** from this study and are not to be taken at any time during the entire study (i.e., from Screening through the Follow-up Period). These exclusions are primarily due to the potential drug interaction profile of the BBR component of HTD1801. Table 4 lists medications known to be strong inhibitors of P-glycoprotein (P-gp), CYP3A4, and CYP2D6; strong inducers of CYP3A4; as well as P-gp substrates with a narrow therapeutic index, and that are prohibited from concomitant use during this study.

Table 4. Prohibited Medications

Single Agents:

| P-glycoprotein | CYP3A4 | | CYP2D6 |
|----------------|-----------------|------------------|-------------|
| clarithromycin | clarithromycin | ritonavir | bupropion |
| erythromycin | telithromycin | saquinavir | fluoxetine |
| amiodarone | troleandomycin | telaprevir | fluvoxamine |
| digitalis | nefazodone | tipranavir | paroxetine |
| dronedarone | St. John's wort | chloramphenicol | quinidine |
| carvedilol | itraconazole | rifampin | terbinafine |
| propafenone | ketoconazole | cobicistat | |
| quinidine | posaconazole | grapefruit juice | |
| ranolazine | voriconazole | conivaptan | |
| verapamil | atazanavir | diltiazem | |
| sildenafil | boceprevir | idelalisib | |
| itraconazole | darunavir | enzalutamide | |
| ketoconazole | indinavir | mitotane | |
| ritonavir | lopinavir | carbamazepine | |
| saquinavir | nelfinavir | phenytoin | |
| telaprevir | | | |
| lapatinib | | | |

Combination Agents:

| P-glycoprotein | CYP3A4 | |
|--------------------------|--|--|
| lopinavir and ritonavir | danoprevir and ritonavir | |
| saquinavir and ritonavir | elvitegravir and ritonavir | |
| tipranavir and ritonavir | indinavir and ritonavir | |
| | lopinavir and ritonavir | |
| | paritaprevir and ritonavir and (ombitasvir and/or dasabuvir) | |
| | saquinavir and ritonavir | |
| | tipranavir and ritonavir | |

Source:

https://www.fda.gov/Drugs/DevelopmentApprovalProcess/DevelopmentResources/DrugInteractionsLabeling/ucm093664.htm (Tables 2-2, 2-3, 3-2, 3-3, and 5-2)

The Investigator should consult the Medical Monitor, as needed, on the concomitant use of any additional medications.

4.7 MANAGEMENT OF CONCOMITANT CONDITIONS

In general, the Investigator should advise subjects to consult their primary care physician as medically warranted.

Specifically for the management of T2DM, the Investigator will instruct study subjects to visit or consult their primary care physician if clinical laboratory results or other symptomatology indicate a hypoglycemic or hyperglycemic state. The Investigator will advise subjects on routine blood glucose monitoring and follow-up with their primary care physician, consistent with the subjects' standard T2DM management practices, as well as instruct subjects to report any signs or symptoms of low or high blood glucose for appropriate management and follow-up.

4.8 LIFESTYLE CONSIDERATIONS

All subjects will receive a hand-out of standard recommendations about lifestyle modification, including, but not limited to: dietary modification, weight loss, exercise, the use of dietary supplements, and alcohol consumption. Subject adherence to diet and lifestyle recommendations will not specifically be assessed.

5.0 EXPERIMENTAL PROCEDURES

5.1 PROCEDURES, MEASUREMENTS, AND EVALUATIONS

Study procedures are summarized across all scheduled study visits as indicated in the Study Design (Figure 1) and the Schedule of Time and Events (Table 1). Unscheduled visits may also occur at any time if medically warranted. Study related assessments performed at all visits will be recorded in the eCRF.

Throughout the study, clinical laboratory (blood and urine) samples will be collected during a fasting state (i.e., at least 8 hours prior to sample collection) and sent to the designated central laboratory for analysis. Study drug should be taken with water and food (e.g., meal or snack).

For subjects who cannot be contacted for either a return for a scheduled clinic visit or for follow-up assessments as described in this section, and who may be considered "lost to follow-up," at least 3 documented attempts should be made to establish contact with and to instruct the subject on how to complete study procedures. In the final attempt to contact the subject, a letter should be sent by certified mail to the subject's last known address.

5.1.1 Screening (Days -28 to -1)

Prior to any clinical procedures and evaluations, written signed informed consent must be obtained. Screening procedures must be completed within 28 days prior to the Baseline visit and can be performed across multiple days during this period. Screening clinical laboratory tests (see Sections 6.2.2 and 6.3.4) may be repeated **once** during Screening if the Investigator believes the results to be erroneous. In the event that Screening tests are repeated, the most current results will be used to determine eligibility. Potential subjects who do not meet all eligibility criteria at Screening will be allowed to re-screen **once** if the Investigator believes that there has been a change in eligibility status. If a potential subject fails to meet eligibility criteria upon re-screen, he/she will remain ineligible for the study.

During Screening, the following procedures must be conducted and assessments obtained. The information will be collected in the investigational site's standard source documents or in source document templates provided by the Sponsor.

- Informed consent
- Confirm eligibility criteria
- Demographic information
- Medical history
- Comprehensive physical examination
- Vital signs
- Weight and height
- 12-lead ECG
- Serum chemistry panel
- Lipid panel
- Hematology with differential

- Coagulation panel
- HbA1c
- HIV and Hepatitis B/C
- G6PD
- Serum pregnancy test (for FOCP)
- FSH test (for postmenopausal females)
- Urine drug test
- MRI-PDFF
- Corrected T1 and T2*
- AEs
- Prior and concomitant medications

Potential subjects who have successfully completed all of the Screening procedures and who have met all the eligibility criteria (see Sections 3.3.1 and 3.3.2) will be eligible for enrollment in the study. Eligible subjects will be instructed to stop all prohibited medications (see Section 4.6) prior to beginning Baseline procedures.

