10.4 PROTOCOL COMPLIANCE

Substantive changes in the protocol include changes that affect the safety of subjects or changes that alter the scope of the investigation, the scientific quality of the study, the experimental design, dosages, assessment variable(s), the number of subjects treated, or the subject-selection criteria. Such changes must be prepared as a protocol amendment by the Sponsor and implemented only upon joint approval of the Sponsor and the Investigator. A protocol amendment must receive IRB/IEC approval before implementation. In parallel with the IRB/IEC approval process, the protocol amendment will be submitted to the appropriate regulatory authority as an amendment to the regulatory submission under which the study is being conducted. If a protocol amendment requires changes in the ICF, the revised ICF prepared by the Investigator must also be approved by the Sponsor, Study Monitor, and the IRB/IEC before implementation.

Departures from the protocol eligibility criteria (see Sections 3.3.1 and 3.3.2) are not permitted as these could jeopardize subject safety, study integrity, or regulatory acceptance of the results.

Departures from other protocol procedures or requirements are allowed only in situations that eliminate an immediate risk to a subject and that are deemed crucial for the safety and well-being of that subject. The Investigator or the attending physician will also contact the Medical Monitor as soon as possible in the case of such a departure. These departures do not require pre-approval by the IRB/IEC; however, the

IRB/IEC and Medical Monitor must be notified in writing as soon as possible after the departure has been made. In addition, the Investigator will document in the subject's eCRF the reasons for the protocol deviation and the ensuing events.

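### Protocol 5.1.1 tells eligible subjects to stop prohibited drugs before Baseline, which contradicts 4.6 and exclusion 19, and no section sets a washout

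*Protocol*

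**What the plan says.** Four places in the protocol govern the drugs in Table 4.

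- **Section 4.6** says they "are not to be taken at any time during the entire study (i.e., from Screening through the Follow-up Period". It gives the reason: "These exclusions are primarily due to the potential drug interaction profile of the BBR component of HTD1801". The list covers strong inhibitors of P-gp, CYP3A4 and CYP2D6, strong CYP3A4 inducers, and "P-gp substrates with a narrow therapeutic index".
- **Exclusion 19** (Section 3.3.2, repeated in the synopsis) excludes "Current use of prohibited medications as described in Section 4.6 of the protocol". It names no time point and no look-back.
- **Section 5.1.1** first says that subjects "who have met all the eligibility criteria (see Sections 3.3.1 and 3.3.2) will be eligible for enrollment in the study". The next sentence is "Eligible subjects will be instructed to stop all prohibited medications (see Section 4.6) prior to beginning Baseline procedures".
- **Section 10.4** adds: "Departures from the protocol eligibility criteria (see Sections 3.3.1 and 3.3.2) are not permitted".

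Under Section 5.1.2, concomitant medications are updated at the Baseline visit before randomization, subjects are told once more to avoid the prohibited drugs, and the first HTD1801 dose is taken at that same visit. The SAP adds nothing on timing; its Section 5.3.3 only codes, lists and summarises medications.

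**The concern.** A subject who is told to stop a prohibited drug at the end of Screening was taking it during Screening. Section 4.6 forbids that, and exclusion 19, judged at Screening, makes the subject ineligible. Either the 5.1.1 sentence applies to no one, or it directs a site to do what two other sections rule out.

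The second reading matters because no interval is attached to it. The ban exists because of interactions with berberine. If the last dose of a listed drug comes just before the first dose of HTD1801, that protection is missing for the first days of treatment. The issue is subject safety in the two active arms.

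**Working it through.** The plan states no figure on this point, so the check is a comparison of the rules followed by day arithmetic.

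**1. Which rules conflict**

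- 4.6 against exclusion 19: consistent if current use is judged at Screening. A user at Screening breaks both.
- 5.1.1 against 4.6: inconsistent. Stopping before Baseline allows use during Screening.
- 5.1.1 against exclusion 19: inconsistent if current use is judged at Screening. If it is judged again at Baseline, a subject who stopped the day before is no longer a current user and passes. That softer reading still contradicts the 4.6 start point.

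So one sentence is out of line with two rules that agree.

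**2. Drug-free interval before the first dose**

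Inputs: Screening is Days -28 to -1 and Baseline is Day 0 (Table 1). On length, 5.1.1 says "Screening procedures must be completed within 28 days prior to the Baseline visit", which is a maximum with no minimum. The first dose is on Day 0 (5.1.2).

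- Acting on 5.1.1: the last prohibited dose is on Day -1, or on Day 0 before procedures begin. Interval: 0 - (-1) = 1 day, or less.
- Following 4.6 and exclusion 19: the interval is at least the length of Screening, whose maximum is 28 days and whose minimum is not stated.

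**3. What such an interval covers**

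The documents give no half-life for any Table 4 drug, so I show a range. Five half-lives are complete in g days if the half-life is at most g/5.

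- g = 1: 1/5 = 0.2 days = 4.8 hours
- g = 7: 1.4 days
- g = 14: 2.8 days
- g = 21: 4.2 days
- g = 28: 5.6 days

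**4. Whether another rule supplies a washout**

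- Exclusion 22 looks back 30 days before Screening, but for unapproved NASH treatments, including UDCA and berberine products.
- Exclusion 24 looks back 30 days or 5 half-lives, whichever is longer, but for investigational drugs.
- Section 4.5 sets a spacing of 1 hour before to 6 hours after each dose. That is not a washout.
- Section 6.3.6 requires medications taken within 28 days of randomization to be recorded and reviewed. It sets no interval.
- Exclusion 25 and consultation of the Medical Monitor are discretionary.

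None fills the gap, although exclusions 22 and 24 show that the same list uses look-backs elsewhere.

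**5. Which drugs could be involved**

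Table 4 single agents: 17 (P-gp) + 30 (CYP3A4) + 6 (CYP2D6) = 53 entries. Seven appear twice, so 53 - 7 = 46 distinct agents. The grouping by class below is mine, not the protocol's. Eleven HIV or hepatitis C antivirals and 4 cancer drugs are largely out of reach under exclusions 5, 6, 15 and 18: 46 - 15 = 31 remain. Of these, 9 are cardiovascular, 5 antidepressant and 2 antiseizure (16 in total). The other 31 - 16 = 15 are 6 antibacterials, 5 antifungals, sildenafil, conivaptan, St. John's wort and grapefruit juice.

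Inclusion 7 requires other permitted regimens to be stable for at least 28 days before randomization. If one of the 16 mainly chronic drugs is swapped for a permitted one, the old drug has then been off for roughly 28 days. The short interval therefore mainly concerns drugs stopped without replacement and short courses.

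**The case against.** The strongest reply is that 5.1.1 cannot be used this way. Its stop instruction goes to subjects who have met every criterion, exclusion 19 included, so it works at most as a reminder. To reach a one-day gap a site must overlook exclusion 19 and the 4.6 start point. This stands in part: the one-day figure is a worst case on a permissive reading. It does not remove the defect. An instruction to stop a drug presumes that the drug is being taken, 5.1.2 treats the instruction as one already given, and the Baseline medication update would pass someone who stopped the day before.

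The harm can also be questioned. Section 4.5 expects no meaningful inhibition of CYP2D6, CYP3A4 or UGT enzymes by HTD1801. Section 1.2.2 reports single doses as safe and well tolerated in healthy subjects in a study covering 0.5-4.0 g, against a largest single dose of 1 g here. A leftover inducer would be expected to lower exposure, so it is a weak safety argument. These points narrow the concern. They do not address narrow-index P-gp substrates, and the healthy-subject result does not show what happens when another drug raises berberine exposure.

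Exclusions 14 and 16 also remove some likely users of the cardiovascular and anti-infective agents, so 31 agents is not a measure of how many subjects are exposed.

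**Conclusion.** The point holds as a contradiction between one sentence in 5.1.1 and two rules that agree with each other, together with a washout that is stated nowhere. Its size is a worst-case interval of one day or less before the first HTD1801 dose. The number of subjects affected is not in the documents and is probably small. The main concerns are narrow-index P-gp substrates and drugs that raise berberine exposure.

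Three stronger readings are tempting and not supported.

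- A reader might infer a three-way conflict. Section 4.6 and exclusion 19 are compatible once current use is judged at Screening.
- A reader might infer that subjects will be harmed. The documents give neither half-lives nor interaction sizes for the Table 4 drugs.
- A reader might infer bias in the efficacy comparison. The same entry rule applies to all three arms before randomization, and no endpoint, analysis or sample size depends on it.

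The conclusion assumes that some sites would act on 5.1.1 as an operating instruction. Five half-lives is a convention taken from exclusion 24; the length of the washout is the sponsor's choice.

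**What to change.** 1. Leave the 4.6 start and end points as they are. Moving the start to the beginning of a washout would loosen the rule: a drug with a half-life of 4.8 hours or less could then be stopped during Screening, one day before dosing.
2. Reword exclusion 19, in 3.3.2 and in the synopsis: *Use of any Section 4.6 prohibited medication at Screening, or within 5 half-lives before randomization (a sponsor-named fixed number of days for grapefruit juice and St. John's wort).*
3. Replace the 5.1.1 stop sentence: *Subjects taking a prohibited medication at Screening are screen failures; they may use the single re-screen once the prescriber has stopped or replaced the drug, the washout is complete, and any replacement meets inclusion 7.*
4. Confirm the washout at the existing Baseline medication update in 5.1.2, before randomization. For half-lives above 28/5 = 5.6 days the washout is longer than the 28-day recording window in 6.3.6, so the site must also ask about earlier use.

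The cost is a few text edits. A few subjects will enter later or re-screen with a repeat MRI. Sample size and analysis do not change.
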